7.2 ASSESSMENT OF SAFETY

The safety of this study will be assessed by an independent DMC. All randomized subjects will be evaluated clinically and using standard laboratory testing during their participation in this study. Safety assessments will consist of monitoring and recording AEs and SAEs; measurements of protocol-specified hematology, clinical chemistry, and other laboratory variables; measurement of protocol-specified vital signs; and other protocol-specified tests that are deemed critical to the safety evaluation of the study drug(s).

7.2.1 Definitions

Adverse Events

An AE is any untoward medical occurrence in a subject administered a pharmaceutical product and which does not necessarily have a causal relationship with this treatment. An AE can therefore be any unfavorable and unintended sign (including a clinically significant abnormal laboratory finding, for example), symptom, or disease temporally associated with the use of an investigational study drug, whether or not considered related to the study drug ([FDA Guidance for Industry 1995](#)).

For the purposes of this clinical study, AEs include events which are either new or represent detectable exacerbations of pre-existing conditions.

Disease progression is not an AE; rather it may be the cause of an AE. The clinical diagnosis that is associated with disease progression must be reported as all other AEs. "Disease progression" should never be used as an AE term.

AEs may include, but are not limited to:

- Subjective or objective symptoms spontaneously offered by the subject and/or observed by the Investigator or study staff including laboratory abnormalities of clinical significance (Note: "clinical significance" is defined as requiring change in study drug dose or discontinuation of study drug or any other medical intervention).
- Any AEs experienced by the subject through the completion of final study procedures.
- AEs not previously observed in the subject that emerge during the protocol-specified AE reporting period, including signs or symptoms associated with CLL that were not present before the AE reporting period.

The following are NOT considered an AE:

- **Pre-existing condition:** A pre-existing condition (documented on the medical history CRF) is not considered an AE unless the severity, frequency, or character of the event worsens during the study period.
- **Preplanned hospitalization:** A hospitalization planned before signing the informed consent form is not considered an SAE, but rather a therapeutic intervention. However, if during the pre-planned hospitalization an event occurs, which prolongs the hospitalization or meets any other SAE criteria, the event will be considered an SAE. Surgeries or interventions that were under consideration, but not performed before enrollment in the study, will not be considered serious if they are performed after enrollment in the study for a condition that has not changed from its baseline level. Elective hospitalizations for social reasons, solely for the administration of chemotherapy, or due to long travel distances are also not SAEs.
- **Diagnostic Testing and Procedures:** Testing and procedures should not be reported as AEs or SAEs, but rather the cause for the test or procedure should be reported.
- **Abnormal laboratory results:** Abnormal laboratory results are not AEs unless they are clinically significant. For example, a clinically significant laboratory result is one that

requires treatment (for example a blood transfusion for low hemoglobin) or requires a change in study drug (eg, lowering the dose or withholding study drug while the laboratory finding resolves or stabilizes).

Serious Adverse Event

Note: The terms “severe” and “serious” are not synonymous. Severity (or intensity) refers to the grade of an AE (see below). “Serious” is a regulatory definition.

A serious adverse event (experience) (SAE) or reaction is any untoward medical occurrence that at any dose:

- Results in death (ie, the AE actually causes or leads to death)
- Is life-threatening (with regards to determining if an AE is serious, “life-threatening” is defined as an AE in which the subject was at risk of death at the time of the event. It does not refer to an event which hypothetically might have caused death if it were more severe. If either the Investigator or the Sponsor believes that an AE meets the definition of life-threatening, it will be considered life-threatening.)
- Requires in-subject hospitalization > 24 hours or prolongation of existing hospitalization
- Results in persistent or significant disability/incapacity (ie, the AE results in substantial disruption of the subject’s ability to conduct normal life functions)
- Is a congenital anomaly/birth defect
- Is an important medical event that may not result in death, be immediately life-threatening or require hospitalization, but may be considered a serious adverse experience when, based upon appropriate medical judgment, the event may jeopardize the subject or subject and may require intervention to prevent one of the other outcomes listed in this definition. Examples of such events are intensive treatment in an emergency room or at home for allergic bronchospasm, blood dyscrasias or convulsion that do not result in hospitalization; or development of drug dependency or drug abuse

Given that the Investigator’s perspective may be informed by having actually observed the event, and the Sponsor is likely to have broader knowledge of the drug and its effects to inform its evaluation of the significance of the event, if either the Sponsor or the Investigator believes that the event is serious, the event will be considered serious.

Suspected Adverse Reaction

The FDA has published a guidance on the reporting of SAEs. This document directs Sponsors to consider more carefully the AEs that are reported in an expedited (urgent) fashion to the FDA. Key elements of this guidance are outlined below:

The guidance defines any AE for which there is a “reasonable possibility” that the drug caused the AE as a Suspected Adverse Reaction.

“Reasonable Possibility”, for the purposes of safety reporting, means there is evidence to suggest a causal relationship between the drug and the AE. Examples of evidence that would suggest a causal relationship between the drug and the AE are:

- A single occurrence of an event that is uncommon and known to be strongly associated with drug exposure (eg, angioedema, blood dyscrasias, rhabdomyolysis, hepatic injury, anaphylaxis, and Stevens - Johnson syndrome).
- One or more occurrences of an event that is not commonly associated with drug exposure, but is otherwise uncommon in the population exposed to the drug (eg, include tendon rupture or heart valve lesions in young adults, or intussusception in healthy infants). If the event occurs in association with other factors strongly suggesting causation (eg, strong temporal association, event recurs on rechallenge), a single case may be sufficiently persuasive; but often, more than one occurrence (from one or multiple studies) would be needed before the Sponsor could make a determination of whether the drug caused the event.
- An aggregate analysis of specific events that can be anticipated to occur in the study population independent of drug exposure. Such events include known consequences of the underlying disease or condition under investigation (eg, symptoms or disease progression), or events unlikely to be related to the underlying disease or condition under investigation, but commonly occur in the study population independent of drug therapy (eg, cardiovascular events in an elderly population). An aggregate analysis (across studies) will identify those events that occur more frequently in the drug treatment group than in a concurrent or historical control group.

This definition of “suspected adverse reaction” and the application of the “reasonable possibility” causality standard is considered to be consistent with the concepts and discussion about causality in the ICH E2A guidance ([FDA Guidance for Industry 1995](#)).

Severity

Definitions found in the Common Terminology Criteria for Adverse Events (CTCAE) version 4.03 or higher will be used for grading the severity (intensity) of nonhematologic AEs. The CTCAE v4.03 displays Grades 1 through 5 with unique clinical descriptions of severity for each referenced AE. Should a subject experience any AE not listed in the CTCAE v4.03 or higher, the following grading system should be used to assess severity:

- Grade 1 (Mild AE) – experiences which are usually transient, requiring no special treatment, and not interfering with the subject’s daily activities
- Grade 2 (Moderate AE) – experiences which introduce some level of inconvenience or concern to the subject, and which may interfere with daily activities, but are usually ameliorated by simple therapeutic measures
- Grade 3 (Severe AE) – experiences which are unacceptable or intolerable, significantly interrupt the subject’s usual daily activity, and require systemic drug therapy or other treatment
- Grade 4 (Life-threatening or disabling AE) – experiences which cause the subject to be in imminent danger of death
- Grade 5 (Death related to AE) – experiences which result in subject death

The grading scale for hematologic toxicity in subjects with CLL is provided in Appendix E.

Causality

The causality of AEs to the study drug will be assessed by means of the question: ‘Is there a reasonable possibility that the event may have been caused by the study drug?’ per FDA guidance on safety reporting requirements ([FDA Guidance 2012](#)).

See [Appendix F](#) for more detail on assessing causality.

Unexpected Adverse Events

An “unexpected” AE is an AE that is not listed in the Investigator Brochure for acalabrutinib, the approved label for ibrutinib, or is not listed at the specificity or severity that has been observed. For example, hepatic necrosis would be “unexpected” (by virtue of greater severity) if the Investigator Brochure referred only to elevated hepatic enzymes or hepatitis. Similarly, cerebral thromboembolism and cerebral vasculitis would be “unexpected” (by virtue of greater specificity) if the Investigator Brochure/package insert listed only cerebral vascular accidents.

"Unexpected" also refers to AEs that are mentioned in the Investigator Brochure as occurring with a class of drugs or as anticipated from the pharmacologic properties of the drug, but are not specifically mentioned as occurring with the study drug under investigation.

7.2.2 Documenting and Reporting of Adverse and Serious Adverse Events by Investigators

The Investigator is responsible for ensuring that all AEs and SAEs that are observed or reported during the study, as outlined in the prior sections, are recorded on the CRF. All SAEs also must be reported using the SAE report form (see "Expedited Reporting Requirements for Serious Adverse Events" later in this section).

7.2.2.1 Adverse Event Reporting Period

After the signing of the ICF and prior to the first dose of study drug, all SAEs must be reported.

After the first dose of study drug, all AEs/SAEs, irrespective of attribution of causality, must be reported.

All adverse events will be reported until 30 days after the last dose of study drug or the start of new anticancer therapy (whichever comes first). After this period, investigators should report serious adverse events or other adverse events of concern that are believed to be related to prior treatment with study drug.

All SAEs that occur during the reporting period should be followed to resolution or until the Investigator assesses the subject as stable or until the subject is lost to follow up or withdraws consent. Resolution/stable means the subject has returned to baseline state of health or the Investigator does not expect any further improvement or worsening of the event.

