An ET visit is required for safety assessments for any subjects who permanently discontinue treatment for any reason, including disease progression. The ET visit should be performed within 7 days of the last dose of all study drugs, if possible, and is not required for subjects who discontinue from the study within 10 days of a scheduled study visit or if the ET visit would be performed within 14 days of the SFU visit.

A SFU visit should be conducted at 30 (+ 7) days after his or her last dose of all study drugs to monitor for resolution or progression of AEs and to document the occurrence of any new events,

regardless of whether the subject receives a new anticancer therapy or demonstrates disease progression within this time frame. Refer to [Appendix A](#) for the assessments required for the ET and SFU visits.

Survival

After progression, subjects will be contacted to assess survival status approximately every 12 weeks until death, withdrawal by subject, lost to follow-up, or study terminated by Sponsor, whichever comes first. At study closure, a survival sweep will be conducted. All subjects who are on study and not known to have died before the survival sweep will be contacted at that time.

Subsequent Anticancer Therapies

After study drug treatment is complete, the following information on subsequent anticancer therapies will be collected approximately every 12 weeks until death, withdrawal by subject, lost to follow-up, or study terminated by Sponsor, whichever comes first:

- Receipt of all subsequent anticancer therapies
- IWCLL indication for initiation of subsequent anticancer therapy
- Response to all subsequent anticancer therapies

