7.2.2.2 Assessment of Adverse Events

Investigators will assess the occurrence of AEs and SAEs at all subject evaluation time points during the study. All AEs and SAEs whether volunteered by the subject, discovered by study personnel during questioning, or detected through physical examination, clinically significant laboratory test (ie, requiring change in study drug dose or discontinuation of study drug or any other medical intervention), or other means will be recorded in the subject's medical record and on the AE CRF and, when applicable, on an SAE/Product Complaint form.

Each recorded AE or SAE will be described by its diagnostic term, duration (ie, start and end dates), severity, regulatory seriousness criteria (if applicable), suspected relationship to study drug, and any actions taken.

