- a. Treatment Period begins with randomization and ends with last dose of study drug. Subjects will take study drug until disease progression or unacceptable toxicity. Subjects will have weekly visits during the first 8 weeks then will have visits every 4 weeks (ie, after Week 8 the next scheduled visit would be at Week 12) through 24 weeks. Thereafter, visits will be every 12 weeks (ie, after Week 24 the next scheduled visit would be at Week 36).
- b. Response evaluations will be done every 12 weeks from Week 1 Day 1 through Week 100, and then every 24 weeks until 5 years on study and then yearly thereafter until disease progression regardless of whether or not a subject has discontinued study drug. Hematology results must be done within 7 days of CT scans. CCI
- c. An early termination visit will be done for subjects who permanently discontinue study drug early for any reason. The safety follow up visit is conducted 30 (+ 7) days after the last dose of study treatment regardless of whether the subject receives a new anticancer therapy or demonstrates disease progression within this timeframe. The ET visit should be performed within 7 days of the last dose of all study drugs, if possible, and is not required for subjects who discontinue from the study within 10 days of a scheduled study visit or if the ET visit would be performed within 14 days of the SFU visit.
- d. CCI
- e. CCI
- f. Hepatitis serology must include hepatitis B surface antigen (HBsAg), hepatitis B surface antibody (HBsAb), hepatitis B core antibody (anti-HBc), and hepatitis C (HCV) antibody. Subjects who are receiving prophylactic intravenous immunoglobulins (IVIG) and have positive HBsAg or anti-HBc must have negative hepatitis B DNA to be eligible. In addition, any subjects testing positive for any hepatitis serology, must have polymerase chain reaction (PCR) testing (see exclusion criterion #15).
- g. Subjects who are anti-HBc positive should be monitored every 3 months with a quantitative PCR test for HBV DNA. Monitoring should continue until 12 months after last dose of study drug(s). Any subject with a rising viral load (above lower limit of detection) should discontinue study drug and have antiviral therapy instituted and a consultation with a physician with expertise in managing hepatitis B.

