#### **4.1.6 Treatment Emergent Period**

The treatment emergent period is defined as the period of time from the date of the first dose of study drug through 30 days after the date of the last dose of study drug or the first date starting new anticancer therapy for CLL, whichever is earlier.

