### 2. Additional Criteria for Narratives:

- Subjects who fulfill ECI (see Appendix 1 for definitions) criteria and additional criteria for narratives as described below:

Note: the window for qualifying events for narratives is from first date of study drug to last date of study drug + 30 days. Beyond this window, narratives should also be provided for any related SAEs and for clinically significant AEs as judged by medical monitor.

ECI Category Name	ECI Subcategory Name	Additional Criteria for Narratives
Cardiac events	Atrial fibrillation	
 
Grade 3 and 4 PT Atrial fibrillation
 
Grade 3 and 4 PT Atrial flutter
 

Hemorrhage	Major hemorrhage	Same as ECI definition. Refer to Appendix 1 Section 2
Hepatotoxicity		Subjects who fulfill biochemical Hy's law criteria defined as below: $\geq 3 \times \text{ULN}$ AST or $\geq 3 \times \text{ULN}$ ALT and $\geq 2 \times \text{ULN}$ total bilirubin where bilirubin increased of $\geq 2 \times \text{ULN}$ either coincides with ALT/AST elevations or follow them within 8 days
Second primary malignancies	Second primary malignancies (excluding non melanoma skin)	Below SMQs excluding PTs mapping to HLT Skin neoplasms malignant and unspecified (excluding melanoma) 
 
SMQ Malignant tumours (including Haematological malignant tumours SMQ and Non- haematological malignant tumours SMQ)
 
SMQ Malignant lymphomas [narrow]
 
SMQ Myelodysplastic syndrome [narrow]
 

Tumor lysis syndrome		Same as ECI definition. Refer to Appendix 1 Section 2

AE=adverse event; ALT=alanine aminotransferase; AST=aspartate aminotransferase; HLT=high-level term; ISS=integrated safety summary; PT=preferred term; SAE=serious adverse event; SMQ=Standardised MedDRA Query; ULN=upper limit of normal.  
MedDRA version 23.0

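### For subjects who start new anticancer therapy within 30 days of last dose, the documents contradict each other on when adverse event collection ends, and the SAP's treatment-emergent window does not match the protocol's cut-off

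*Protocol*

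**What the plan says.** Protocol Section 7.2.2.1 has all adverse events reported "until 30 days after the last dose of study drug or the start of new anticancer therapy (whichever comes first". Its next sentence sets what continues afterwards: "investigators should report serious adverse events or other adverse events of concern that are believed to be related to prior treatment with study drug".

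Protocol Section 7.1 requires a safety follow-up visit 30 (+7) days after last dose. One stated purpose is "to document the occurrence of any new events", and this applies "regardless of whether the subject receives a new anticancer therapy or demonstrates disease progression within this time frame". Appendix A, footnote c, repeats the timing: the visit is "conducted 30 (+ 7) days after the last dose of study treatment regardless of whether the subject receives a new anticancer therapy". The synopsis says the same. Section 7.2.2.2 adds: "Investigators will assess the occurrence of AEs and SAEs at all subject evaluation time points during the study".

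In the SAP, Section 4.1.6 ends the treatment-emergent period 30 days after last dose "or the first date starting new anticancer therapy for CLL, whichever is earlier". Section 8.1.2 has events of clinical interest reported during treatment and during follow-up, including the phase after progression. Appendix 1 lists atrial fibrillation and infections among those events. Appendix 2 states that "the window for qualifying events for narratives is from first date of study drug to last date of study drug + 30 days", with no cut-off at new therapy.

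SAP Sections 2.6 and 7.2.1 place treatment-emergent atrial fibrillation and Grade ≥3 infections first and second in the fixed testing sequence that follows PFS non-inferiority.

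**The concern.** A site whose subject stops study drug and begins another anticancer therapy a few days later has two instructions. One ends all-cause reporting on the day the new therapy starts. The other has the site see the subject about a month after last dose and document whatever is new. Sites may resolve this differently, and where the cut-off is applied, an open-label investigator's view of causality decides what is still reported.

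The second issue concerns the tested endpoints. The protocol's cut-off is any new anticancer therapy, whereas the SAP's is new therapy for CLL. Where the new therapy is for another cancer, the SAP keeps the subject at risk for atrial fibrillation and Grade ≥3 infection over days on which the protocol's reporting rule no longer requires full collection.

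**Working it through.** No sample size, power or event figure in the plan rests on this point, so the check is a comparison of texts.

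| Place | What it governs | End point after last dose | Effect of new therapy |
|---|---|---|---|
| Protocol 7.2.2.1 | Reporting of all AEs | Day 30 | Ends at any new anticancer therapy; related SAEs and related AEs of concern continue |
| Protocol 7.1, safety follow-up visit | Documenting new events | Day 30 (+7) | None |
| Protocol 7.2.2.2 | AE assessment and recording | Every evaluation during the study | None |
| Appendix A footnote c; synopsis | Visit timing only | Day 30 (+7) | None |
| SAP 8.1.2 | Reporting of events of clinical interest | Through follow-up | None |
| SAP 4.1.6 | Analysis window | Day 30 | Ends at new therapy for CLL only |
| SAP Appendix 2 | Narrative selection window | Day 30 | None |

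The collection conflict is therefore 7.2.2.1 against 7.1 and 7.2.2.2, with SAP 8.1.2 on the side of longer collection. SAP 4.1.6 and Appendix 2 are not collection rules, but they depend on what is collected.

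Three hypothetical subjects show where it matters.

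1. *Stops for progression, starts new CLL therapy on day 5, has a Grade ≥3 infection on day 12 considered unrelated.* Reporting is not required under 7.2.2.1. The event is to be documented under 7.1 and reported under SAP 8.1.2. Under SAP 4.1.6 it is not treatment-emergent, so it stays out of the tested endpoint whichever rule the site follows. The effect is on the completeness of AE and SAE reporting. A narrative would follow only if another criterion is met, such as seriousness, because infections are not in the additional-criteria table of Appendix 2.
2. *Stops for a second cancer needing systemic treatment (a listed reason in Protocol 8.1), starts that treatment on day 5, has atrial fibrillation on day 12 considered unrelated.* Reporting is not required under 7.2.2.1. Because the treatment is not for CLL, SAP 4.1.6 keeps the window open to day 30. That leaves 30 − 5 = 25 days that count towards a tested endpoint without an all-cause reporting obligation.
3. *As in 2, but the event is serious and believed related.* It is reportable under 7.2.2.1. No gap arises.

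There is one edge case. Protocol 6.3.4 allows study drug to be continued after curative treatment of a second cancer, subject to discussion with the medical monitor. Read literally, 7.2.2.1 would then end all-AE reporting while the subject is still on study drug.

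For size, a subject who starts new therapy *s* days after last dose has 30 − *s* affected days, at most about 30. To turn this into events one needs the number who switch, the distribution of *s*, the event rate in that period, the share considered unrelated, and the share of sites applying the cut-off. The documents give none of these for this trial.

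**The case against.** Several points on the other side are sound.

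- **Much is still captured.** Related SAEs and related AEs of concern remain reportable with no time limit. Section 7.2.2.3 requires ventricular arrhythmias to be reported whatever the causality and sets no end date of its own. Deaths are picked up by survival follow-up. A site may record everything else at the follow-up visit. This stands, and it limits the problem to events considered unrelated (or related but neither serious nor of concern).
- **Ending at new therapy is a coherent choice.** It limits attribution of the next drug's toxicity to study drug, and SAP 4.1.3 and 4.1.6 do likewise for CLL therapy. This stands for analysis. It is a weaker argument for collection, because an analysis window can be applied to fuller data but not the reverse.
- **The sentence can be parsed otherwise.** Grammatically, the 30 days could run from the earlier of last dose and new therapy. Since study drug normally stops first, the mention of new therapy would then do almost nothing, so the cut-off reading is the natural one. The ambiguity is a further reason to clarify.
- **The rule is recent.** The amendment log shows that 7.2.2.1 was updated in this amendment, and the log also says enrolment had ended. The text in force before it is not in the documents. This stands: one cannot say how events in subjects who switched before then were collected.

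A reader might infer that AEs and SAEs within 30 days of last dose are simply lost once a subject switches. The documents do not support that, for the reasons in the first point. The supported statement is inconsistent capture.

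A reader might also attempt a count. Assume 200 of 500 subjects switch, on average on day 7, so 23 days each: 200 × 23 / 30.4375 ≈ 151 person-months. Spread the 26% Grade ≥3 infection rate quoted for ibrutinib in CLL over the 9.4-month median follow-up of the randomised ibrutinib-versus-ofatumumab trial: −ln(1 − 0.26)/9.4 ≈ 0.032 per month. The product is about 5 infections, or about 14 if the rate is tripled. This does not measure the problem. The number, timing and multiplier have no source, and joining 26% to 9.4 months is itself an assumption. The count includes related serious infections, which are still reported. It also treats all switchers alike, although SAP 4.1.6 excludes later events after new CLL therapy from the tests.

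**Conclusion.** The contradiction is real and should be reconciled. For subjects who start new anticancer therapy within 30 days of last dose, Protocol 7.2.2.1 and 7.1 give different ends to AE collection, and SAP 8.1.2 assumes the longer one for events of clinical interest. Separately, the tested atrial fibrillation and Grade ≥3 infection endpoints use a window that, after non-CLL anticancer therapy, runs past what 7.2.2.1 obliges sites to collect.

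The effect on the tested endpoints is probably small: it is confined to subjects treated for another cancer within 30 days of last dose, and to events that 7.2.2.1 does not otherwise keep reportable. That is a judgement, since the documents do not size this group. For subjects who switch to CLL therapy, the effect is on AE and SAE reporting and on the data available for narratives. It would be tempting to infer a bias between arms because stopping and switching could differ by arm, but nothing in the documents shows that they do.

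**What to change.** Amend Protocol 7.2.2.1 so that all AEs and SAEs, irrespective of causality, are collected until 30 days after last dose whether or not new anticancer therapy has started, and leave the following sentence on later related events as it is. This agrees with 7.1, 7.2.2.2 and the SAP narrative window. Align SAP 8.1.2 with the protocol on how long events of clinical interest are collected.

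Keep SAP 4.1.6 as it stands. Use the recorded start date and indication of the new therapy to exclude later-onset events after new CLL therapy from the TEAE tables and tested endpoints, and list those events separately.

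For data already collected, list by arm the subjects who started non-CLL anticancer therapy within 30 days of last dose, with start dates and any atrial fibrillation or Grade ≥3 infection recorded afterwards. State in the study report that all-cause collection in that interval may be incomplete.

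The cost is one protocol sentence, a short SAP clarification and matching CRF guidance. The visit already takes place, Protocol Section 4 already records start dates of subsequent anticancer therapy, and Section 7.1 documents concomitant medication to at least 30 days after last dose. There are two drawbacks. Some events caused by the new therapy will be recorded, though the start date identifies them. The change also works only prospectively and cannot recover events already missed.
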